#### 3. OBJECTIVES

#### 3.1 Primary Objective

The primary aim is to determine whether the normoxic target leads to a lower cumulative daily delta SOFA score (CDDS) from day 1 to day 14 as compared to the hyperoxic group. For detailed calculations and justification of the CDDS endpoint, see section 10.2

## 3.2 Secondary Objective(s)

The secondary aims are to compare total maximum SOFA score (=total of the most deranged score of each organ system during ICU stay), total maximum SOFA score - SOFA score on admission, SOFA rate of decline, hypoxic episodes ( $PaO_2 < 55 \text{ mmHg}$ ), vasopressor / inotrope requirements (max dose every 24 hours), need for renal replacement therapy and fluid balances (every 24 hours) between the normoxic and the hyperoxic groups. Furthermore, we will determine whether oxidative stress parameters F2-isoprostanes (on day 1,2, and 4) and as clinical endpoints: duration of mechanical ventilation, lung injury score, ventilator-free days, length of stay (in ICU, in hospital) and mortality (ICU and hospital) are different between both groups. Interim analyses will take place after inclusion of 100 patients and 250 to detect possible differences in mortality.

## Feasability endpoint:

Time spent in the assigned PaO2 range

## Subgroup

To further investigate the circulatory changes due to differences in oxygen suppletion, we will study additional parameters in a subgroup of 40 patients, which are too time-consuming to be performed in the whole group. We will estimate hemodynamics by PICCO (C.I., SVRI, extravascular lung water), microcirculation by sublingual Sidestream Dark Field imaging, and body fluid status by bio-impedance on day 1, 2 and 4.

## 4. STUDY DESIGN

Design:	randomized, clinical multicenter trial
Duration:	24 -30 months
Setting:	Intensive Care Units of VU University Medical Center, Academic Medical
	Center, Tergooiziekenhuizen, Slotervaartziekenhuis, Medisch Centrum
	Alkmaar and Sint Franciscus Gasthuis.

#### **5. STUDY POPULATION**

#### 5.1 Population (base)

The study population consists of patients admitted to the Intensive Care Units of the VU University Medical Center, Academic Medical Center, Tergooiziekenhuizen, Slotervaartziekenhuis, Medisch Centrum Alkmaar and Sint Franciscus Gasthuis.

#### 5.2 Inclusion criteria

In order to be eligible to participate in this study, a subject must meet all of the following criteria:

- Age ≥18 years
- ≥2 positive SIRS-criteria:

Temperature >38°C or hypothermia <36°C

Heart rate >90 bpm

Respiratory rate >20 /min or pCO2 <32 mmHg (4.3 kPa)

Number of leucocytes >12 x 109/l of <4 x 109/l of >10% bands

- Within 12 hours of admittance to the ICU

- Expected stay of more than 48 hours as estimated by the attending physician

### 5.3 Exclusion criteria

A potential subject who meets any of the following criteria will be excluded from participation in this study:

- Elective surgery
- Carbon monoxide poisoning
- Cyanide intoxication
- Methemoglobinemia
- Sickle cell anemia
- Severe pulmonary arterial hypertension (WHO class III or IV)
- Known severe ARDS (PaO2/FiO2 ≤100 mmHg and PEEP ≥ 5 H2O)
- Known cardiac right to left shunting
- Pregnancy
- Severe COPD (Gold class III or IV) or other severe chronic pulmonary disease

#### 5.4 Sample size calculation

Power calculations are based on mean delta SOFA scores, which are invariably reflected in CDDS.

The trial is designed to detected a difference of 0.33 standard deviation (SD) on the primary endpoint with 90% power and a 2-sided alpha of 0.05, with 2 interim analyses.

The trial will be stopped if there is evidence for outcome differences in either direction. Alpha

spending for the interim analyses is approximated with a Lan-DeMets O'Brien-Fleming

spending function. The total sample size thus needed is 385 patients.

Hyperoxia and SIRS ("O2-ICU")

## 6. TREATMENT OF SUBJECTS

#### 6.1 Investigational product/treatment

In this study we will investigate 2 groups with PaO2 targets both within the range of current practice:

Group 1: target PaO2 120 (105 - 135) mmHg (hyperoxic)

Group 2: target PaO2 75 (60 - 90) mmHg (normoxic)

The oxygenation goals are the long-term  $PaO_2$  targets for the participant's entire stay in the ICU.

We will not use excessive measures to achieve the PaO2 targets in group 1. For patients with mechanical ventilation excessive measures include FiO2 settings of >0.60 or prone position. For patients who are not intubated excessive measures include non-invasive mechanical ventilation or intubation. For patients who will not be able to achieve the PaO2 targets of their group, PaO2 targets will be determined by the treating physicians feasible with conventional measures not including those mentioned above. Temporary measures to improve oxygenation for planned procedures involving upper airways such as tracheostomy, bronchoscopy etc will follow standard practices of the participating centers. These aberrations from study targets will be limited to the shortest duration possible.

**6.2 Use of co-intervention (if applicable)** Not applicable

## 7. INVESTIGATIONAL PRODUCT

### **7.1 Name and description of investigational product(s)** Oxygen

## 7.2 Summary of findings from clinical and non-clinical studies with known and potential risks and benefits

Animal and human studies indicate that hyperoxia (mostly severe hyperoxia with PaO2 > 300 mmHg after a period of ventilation with an FiO2 of 100%) can lead to important circulatory effects. The hypothesis is that hyperoxia causes vasoconstriction in the microcirculation with a loss of functional capillary density and disturbed microvascular flow.  Vasoconstriction causes an increase in systemic vascular resistance and a reduction of the cardiac output.   This loss of perfusion has been suggested to outweigh higher arterial oxygen content, resulting in a net loss of oxygen delivery and an increase of ischemia/reperfusion injury.

In patients with myocardial or cerebral infarction, hyperoxia increases infarct size and mortality, and in patients after cardiac arrest hyperoxia is associated with worse functional outcome and increased mortality. 

Up until now, no prospective, randomized controlled studies investigating the effect of hyperoxia in ICU patients have been performed. A recent large retrospective study showed an independent association between both low and high PaO2 with in-hospital mortality . However, another retrospective study  did not find this association.

#### 7.3 Description and justification of route of administration and dosage

Fraction of inspired oxygen (FiO2) which is applied to the patient by the mechanical ventilator or oxygen suppletion by nasal cannula or oxygen mask.

#### 7.4 Dosages, dosage modifications and method of administration

In this study we will investigate 2 groups with PaO2 targets both within the range of current practice:

Group 1: target  $PaO_2$  at ICU 120 (105 – 135) mm Hg Group 2: target  $PaO_2$  at ICU 75 (60 – 90) mmHg The oxygenation goals are the long-term PaO2 target for the participant's entire stay in the ICU.

We will not use excessive measures to achieve the PaO2 targets in group 1. For patients with mechanical ventilation excessive measures include FiO2 settings of >0.60 or prone

position. For patients who are not intubated excessive measures include non-invasive mechanical ventilation or intubation. For patients who will not be able to achieve the PaO2 targets of their group, PaO2 targets will be determined by the treating physicians feasible with conventional measures not including those mentioned above. Temporary measures to improve oxygenation for planned procedures involving upper airways such as tracheostomy, bronchoscopy etc will follow standard practices of the participating centers. These aberrations from study targets will be limited to the shortest duration possible.

#### 7.5 Preparation and labelling of Investigational Medicinal Product

Not applicable

7.6 Drug accountability Not applicable

## 8. METHODS

#### 8.1 Study parameters/endpoints

#### 8.1.1 Main study parameter/endpoint

The primary endpoint will be cumulative daily delta SOFA score (CDDS) from day 1 to day 14. For detailed calculations and justification of the CDDS endpoint, see section 10.2

#### 8.1.2 Secondary study parameters/endpoints

Secondary parameters will include total maximum SOFA score (= total of the most deranged score of each organ system during ICU stay), total maximum SOFA score - SOFA score on admission, SOFA rate of decline, hypoxic episodes ( $PaO_2 < 55 \text{ mmHg}$ ), vasopressor / inotrope requirements (max dose every 24 hours), need for renal replacement therapy and fluid balances (every 24 hours). Furthermore, oxidative stress parameters F2-isoprostanes will be determined (on days 1, 2 and 4) and as clinical endpoints: duration of mechanical ventilation, ventilator-free days, length of stay (in ICU, in hospital) and mortality (ICU and hospital). Interim analyses will take place after inclusion of 100 patients to detect possible differences in mortality.

The amount, modality and duration of oxygen administered prior to ICU admission will be recorded. This will be treated as a potential effect-modifying variable and reported in the baseline characteristics.

#### 8.1.3 Feasibility endpoint

Time spent in the assigned PaO2 range

#### 8.1.4 Subgroup

To further investigate the circulatory changes due to differences in oxygen suppletion, we will study additional parameters in a subgroup of patients, which are too time-consuming to be performed in the whole group. We will estimate hemodynamics by PICCO (C.I., SVRI, extravascular lung water), microcirculation by sublingual Sidestream Dark Field imaging, and body fluid status by bio-impedance.

a) Arterial blood gas analysis with  $PaO_2$  and lactate measurement will be determined initially at least every 4 hours, and at least every 6 hours after stabilisation. Data will be collected during the entire stay on the ICU. Area under the curve will be calculated for  $PaO_2$ ,  $O_2$ saturation, FiO2 and lactate.

#### b) Hemodynamics

Whenever patients for more intensive hemodynamic monitoring are provided with continuous cardiac output measurement by Swan Ganz catheter or PiCCO, SVRI, CO and CI and EVLW will be measured every 4 hours. In all patients with a central line in the jugular vein, SvO2 will be determined daily.

e) Sublingual mucosal microcirculation measurements will be performed on day 1, 2, and 4 using sidestream dark field (SDF) imaging and quantified as the level of perfused small vessel density and microvascular flow index (vessel diameter <  $20 \mu$ m).

- f) Bio-impedance measured resistance/reactance/impedance at day 1, 2, and 4.
- g) Diaphragm dysfunction will be quantified (and compared between groups) using electromyography (Edi) and ultrasonography (diaphragm thickness, thickening fraction) at days 1, 2 and 4.

#### 8.2 Randomisation, blinding and treatment allocation

Randomisation will be performed with the use of randomisation list generated by a webbased computer program

#### 8.3 Study procedures

- 5) Deferred consent by patient representative
- 6) Routine clinical data (demographic characteristics, reason of admission, comorbidity, APACHE II)
- Titration of FiO2, based on measured PaO2 group 1: target PaO2 at ICU of 120 (105 – 135) mm Hg group 2: : target PaO2 at ICU of 75 (60 – 90) mmHg
- 8) Blood sample collection at baseline and on day 2, and 4 for determination of parameters of oxidative stress and tissue/organ perfusion (*in total 40 ml extra for study*). Remaining blood material after analysis will be stored for additional analyses in the future.

#### Substudy

In a subgroup of 100 patients, hemodynamics will be more intensively monitored by SDF, PiCCO and bio-impedance. Diaphragm function will be measured using electromyography (Maquet NAVA® feeding tube or similar) and ultrasonography at days 1, 2 and 4. Ultrasonography of heart and lungs (and diaphragm) is part of routine ICU treatment. Patients who do not need a feeding tube will not be eligible for inclusion in the substudy. These additional measurements will only be done in a subgroup of patients because they are very time consuming and it is logistically impossible to perform them in all the patients.

#### 8.4 Withdrawal of individual subjects

Subjects can leave the study at any time for any reason if they wish to do so without any consequences. The investigator can decide to withdraw a subject from the study for urgent medical reasons.

#### 9. SAFETY REPORTING

#### 9.1 Section 10 WMO event

In accordance to section 10, subsection 1, of the WMO, the investigator will inform the subjects and the reviewing accredited METC if anything occurs, on the basis of which it appears that the disadvantages of participation may be significantly greater than was foreseen in the research proposal. The study will be suspended pending further review by the accredited METC, except insofar as suspension would jeopardise the subjects' health. The investigator will take care that all subjects are kept informed.

#### 9.2 SAEs and SUSARs

This study compares two treatment targets that are used in standard care. All included patients are admitted to the Intensive Care with a life-threatening disease. Any major adverse development can be expected as part of the underlying disease. Therefore, it is not achievable to report all these developments individually as SAEs. Every three months we will send a line-listing of all SAEs to the METc. Furthermore, all deaths will be reported via ToetsingOnline to the METc/CCMO within one week of the event.

#### 9.3 Data Safety Monitoring Board (DSMB) / Safety Committee

Since the titration of  $FiO_2$  based on the measured  $pO_2$  is within the range of standard care, we do not expose the patients to additional risk. Therefore a data safety monitoring board will not be instituted.

#### **10. STATISTICAL ANALYSIS**

#### **10.1 Descriptive statistics**

Statistical analysis will be performed using the SPSS statistical software package (SPSS Inc.®, Chicago USA). All included patients will be incorporated in the statistical analysis. Descriptive statistics of these quantitative data will include mean, median, standard deviation and interquartile range.

## 10.2 Primary and secondary study parameter(s)

#### **Calculations of CDDS primary endpoint**

The primary endpoint will be *cumulative daily delta SOFA score* (CDDS) from day 1 to day 14, calculated as:

$$CDDS = \sum_{i=day2to14} (SOFA_{DAYi} - SOFA_{ADMISSION})$$

or alternatively,

$$CDDS = SOFA_{DAY2} + SOFA_{DAY3} + SOFA_{DAY4} + \dots etc + SOFA_{DAY14} - (13 \cdot SOFA_{ADMISSION})$$

Daily SOFA score is calculated as the total of maximum scores for each organ system excluding respiratory system (because of possible PaO2/FiO2 distortion). For patients discharged from the ICU, SOFA score will be registered as 0 from the day of discharge to day 14. Death in the ICU will be registered as a score of 20 (maximum) from the day of death to day 14.

CDDS reflects a balanced weighting of the following clinically relevant preconditions:

- 7. Low (or negative) delta SOFA score is better than high (or positive) delta SOFA score.
- 8. Shorter duration of ICU stay is better than longer stay.
- 9. Discharge from the ICU is better than death in the ICU.
- 10. Eventual discharge after a high admission SOFA score is better than discharge after a low admission SOFA score.
- 11. Eventual death after a low admission SOFA score is worse than discharge after a high admission SOFA score.
- 12. Early SOFA score reduction is better than late SOFA score reduction.

Other possible endpoints (such as *delta SOFA score* or *SOFA rate of decline*) fail to satisfy most of these criteria.

The differences of primary and secondary parameters between the 2 groups will be calculated by intention-to-treat analysis. The primary endpoint (CDDS) is designed and

tested as a tool for ranking outcomes. The between-group comparison on the primary endpoint will therefore be made using the Wilcoxon rank-sum test.

Secondary outcomes will be compared using ANOVA for repeated measurements, Chi-Squared, Mann-Whitney U or Fisher's Exact test where appropriate. Mortality will be assessed with the Kaplan Meier and log rank test.

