#### 11.2 Recruitment and consent

#### 11.2.1. Deferred consent

For this study we ask for deferred consent and we appeal to the emergency procedure for consent in medical research as stated in article 6, paragraph 4 of the WMO because of the following reasons.

Oxygen suppletion is applied to almost all ICU-patients. To alleviate respiratory distress oxygen therapy is initiated and cannot be postponed. Patients admitted to an Intensive Care Unit (ICU) are mostly incompetent to give informed consent. Obtaining informed consent from a legal representative takes time (on average up to 12 hours), even by an experienced research team.

We propose to randomize each patient who meets the inclusion criteria ultimately within 2 hours after ICU admission. Oxygenation targets according to randomization are applied immediately thenceforth. Informed consent from the legal representative will be requested as soon as possible thereafter, but never later than 24 hours after randomization. If informed consent is not obtained within those 24 hours, or if a legal representative denies participation within this time frame, the patient is excluded and data will no longer be used. Thenceforth the patient is oxygenated according to the policy of the attending physician.

During hospital admission, we will attempt to achieve informed consent from the patients themselves. If this was not possible (*for example* due to incomplete neurological or physical recovery, or due to early transfer to another hospital) we will send a letter to the patients to inform them that we would like to use the data and blood samples obtained during the study. If they don't want their data to be used, they can contact us by the telephone numbers or email addresses we have provided in the letter. We will not send this letter to the patients who cannot recover sufficiently to understand the letter and take a considered decision about the study.

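### The CDDS gives a patient who dies on the ward by day 14 the same score as one discharged alive, so the primary ranking misses these deaths

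*Supplement*

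**What the plan says.** The primary endpoint in section 10.2 adds up daily SOFA (without the respiratory component) minus admission SOFA over days 2 to 14. Two sentences settle what happens once a patient is no longer under observation in the ICU.

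- On discharge: "For patients discharged from the ICU, SOFA score will be registered as 0 from the day of discharge to day 14". This carries no condition on survival, organ function or destination.
- On death, the rule reaches only as far as the ICU: "Death in the ICU will be registered as a score of 20 (maximum) from the day of death to day 14".

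No other section gives a score for death on the ward, readmission to the ICU, or transfer to another ICU.

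The same section lists six orderings that the CDDS is meant to respect. The third is "Discharge from the ICU is better than death in the ICU", which does not place ward death. The fifth says that eventual death after a low admission score is worse than discharge after a high one, and it is not limited to death in the ICU. The test follows from the ranking purpose: "The between-group comparison on the primary endpoint will therefore be made using the Wilcoxon rank-sum test".

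Deaths on the ward enter only through hospital mortality, a secondary endpoint (8.1.2). Section 11.2.1 foresees that a patient's own consent may be missed, among other reasons, "due to early transfer to another hospital"; no CDDS rule accompanies this.

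**The concern.** The CDDS is justified as a tool for ranking outcomes, so its ordering has to be right. Under the stated rule a ward death is ordered as a recovery. This is not a missing detail: applying the text exactly produces the wrong rank.

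If ward deaths are equally common in both arms, misranking them mainly dilutes a true difference. If they differ by arm, the primary test does not see that difference. Section 8.2 describes no blinding of treatment and oxygen is titrated to measured PaO2, so treating staff presumably know the arm, and the timing of ICU discharge could differ by arm. The futility bound in 10.3 and its worked example of stopping at 275 patients are both stated on the primary endpoint, so the misranking would reach those decisions too.

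**Working it through.** **Inputs.** From 10.2: CDDS = (sum of SOFA on days 2 to 14) - 13 × admission SOFA, with 0 per day from ICU discharge and 20 per day from death in the ICU. Lower is better. From 5.4: a design difference of 0.33 SD. The plan gives no figure of its own for ward deaths, so there is none to reproduce. The sample size is not in dispute.

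**Step 1: the same patient, alive or dead.** Admission SOFA 10, day 2 = 8, day 3 = 7, ICU discharge on day 4.
- Survives: 8 + 7 + 11 × 0 - 130 = -115.
- Dies on the ward on day 6, as written: again -115.
- Dies on day 6, scored 20 on days 6 to 14: 8 + 7 + 2 × 0 + 9 × 20 - 130 = +65.

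**Step 2: place of death alone.** Admission SOFA 8, with 8 on every ICU day.
- Discharge on day 5, ward death on day 6: 3 × 8 - 104 = -80.
- Death in the ICU on day 6: 4 × 8 + 9 × 20 - 104 = +108.
- Discharged alive on day 10: 8 × 8 - 104 = -40, which ranks worse than the ward death.

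**Step 3: the protocol's fifth ordering.**
- A: admission SOFA 6, 6 on days 2 and 3, discharge on day 4, dies on the ward: 12 - 78 = -66.
- B: admission SOFA 10, 10 on days 2 to 9, discharged alive on day 10: 80 - 130 = -50.

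A died after a low admission score and B was discharged after a high one, yet A ranks better. The ordering fails.

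**Step 4: readmission and transfer.** Read literally, the rule keeps a readmitted patient at 0 to day 14, whatever the observed SOFA. For a transfer to another ICU on day 4, with admission SOFA 10 and 9 on days 2 and 3, treating the transfer as discharge gives 18 - 130 = -112. If 9 persisted to day 14 the score would be 13 × 9 - 130 = -13. Which applies is open, because ICU discharge is not defined.

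**Step 5: rough size in ranks, under assumptions.** The documents give no event rates. An illustrative simulation assumed 20% ICU death, ward death of 2%, 5% or 10%, admission SOFA with mean 8 and SD 3, a median ICU stay of about 5 days, and ward death 1 to 4 days after discharge. Ward deaths and survivors shared the same discharge pattern by construction.

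| Group | Mean rank percentile |
|---|---|
| Survivors | 0.40 |
| Ward deaths, as written | 0.40 |
| Ward deaths, scored 20 from day of death | 0.75 to 0.78 |
| ICU deaths | 0.90 |

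As written, about 62% of ward deaths ranked better than the median. For normal data, 0.33 SD corresponds to a rank-sum probability of Φ(0.33/√2) = 0.592, a shift of 0.092 from 0.5. For an assumed imbalance of 2 to 5 percentage points between arms:
- Extra ward deaths among patients who would otherwise have been discharged alive on the same day: the planned statistic moves by 0. The amount missed is 0.02 × (0.75 - 0.40) = 0.007 up to 0.05 × (0.78 - 0.40) = 0.019.
- Ward deaths in place of ICU deaths: the arm is credited with 0.02 × (0.90 - 0.40) = 0.010 up to 0.05 × 0.50 = 0.025, with no fewer deaths.

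**The case against.** The strongest case on the other side is that the oxygen targets apply to the ICU stay, and that the protocol deliberately sets ICU discharge against ICU death. Mortality is also examined separately: hospital mortality is a secondary endpoint, a Kaplan-Meier and log-rank analysis is planned, the interim looks consider mortality, and all deaths are reported within a week (9.2). An excess of ward deaths would be seen. That stands as a safeguard for interpretation, but none of it changes the primary ranking.

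Three stronger readings are tempting, and the documents do not support them.

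- A reader might infer that any harm through ward deaths counts as benefit for that arm. It does not: a ward death scores the same as a live discharge on that day, so turning ward survivors into ward deaths leaves the CDDS unchanged. Credit arises only when ward death or early discharge replaces an ICU death or a longer ICU stay.
- A reader might infer that patients transferred in organ failure are definitely scored as recovered. Section 11.2.1 mentions hospital transfer only in connection with consent. It says nothing of transfer to an ICU, continuing organ failure or timing before day 14, and whether such a transfer is an ICU discharge is undefined.
- A reader might set the 180-point gap in step 1 against the design difference. That compares one patient's score with a difference between group means. The test uses ranks, which bounds one patient's influence, and the documents give no SD in points.

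**Conclusion.** The concern holds for ward death, directly from the text of 10.2: a death on the ward by day 14 is scored as a live discharge, and it can rank above a survivor, against the protocol's own fifth ordering. For readmission the literal rule gives 0. For transfer to another ICU the score is either 0 or undefined.

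The error in an individual score is large (-115 against +65 in the worked case). The net effect on the trial is unknown and may be modest. In the illustration a 2-point imbalance is worth about 0.007 to 0.010 on the rank-sum probability, at most about one-ninth of the design shift of 0.092, and a 5-point imbalance at most 0.025. Those sizes rest on assumed rates, ICU stays and times of death; the -115, +65, -66 and -50 do not. With equal rates in both arms the main consequence is dilution.

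**What to change.** In 10.2, before any comparison by arm:

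- Score 20 from the day of death to day 14 for death anywhere by day 14.
- Score 0 only on days when the patient is alive and out of any ICU.
- On readmission, use the observed SOFA.
- Define ICU discharge. For transfer to another ICU, use the receiving unit's SOFA where available, with a sensitivity analysis for the rest. Carrying the last value forward is one bound and 0 is another; neither should be the sole rule, since carrying forward freezes a patient who may be improving.

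The change does not guarantee that every death ranks below every survivor. Patient A in step 3, dying on day 14, would score 12 + 20 - 78 = -46, only just worse than B at -50. Late deaths in the ICU already have this property. The change makes ward deaths consistent with ICU deaths and no more.

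The cost is one paragraph, plus dates of ward death and SOFA on readmission for what should be a small number of patients. Hospital mortality, a survival analysis and reporting of all deaths are already planned, so most death dates should be at hand. SOFA from receiving units may be harder to obtain.

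### The primary rank-sum test on CDDS is valid but unadjusted; a prespecified baseline-adjusted rank analysis would use data the trial already holds, for a gain in power that is likely but of uncertain size

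*Supplement*

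**What the plan says.** The references are to the final protocol (version 10).

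- **Endpoint (10.2).** CDDS is the sum of SOFA on days 2 to 14 minus 13 times admission SOFA, without the respiratory component. Days after ICU discharge count 0. For deaths: "Death in the ICU will be registered as a score of 20 (maximum) from the day of death to day 14".
- **Intended ranking (10.2).** One listed precondition is "Eventual discharge after a high admission SOFA score is better than discharge after a low admission SOFA score".
- **Test (10.2).** CDDS is described as designed and "tested as a tool for ranking outcomes". It follows that "The between-group comparison on the primary endpoint will therefore be made using the Wilcoxon rank-sum test". No covariate, stratum or adjusted sensitivity analysis is named.
- **Baseline data (8.3).** The trial records "Routine clinical data (demographic characteristics, reason of admission, comorbidity, APACHE II"). Admission SOFA is needed for the endpoint, and centre is known because the trial is multicentre. Section 2 already names sepsis, trauma/haemorrhage and post-resuscitation as subgroups.
- **Randomisation (8.2).** The whole description is: "Randomisation will be performed with the use of randomisation list generated by a webbased computer program". No stratification factor is mentioned.
- **Power (5.4).** The design targets "a difference of 0.33 standard deviation (SD) on the primary" endpoint with 90% power, two-sided alpha 0.05, two interim analyses and 385 patients. No SD, baseline correlation or R² is given.

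**The concern.** Admission SOFA is set before treatment and enters the score with a fixed weight of −13. A patient discharged on day 2 scores exactly −13 × admission SOFA: −39 at SOFA 3 and −130 at SOFA 10. Such an early discharge is extreme in a population selected for an expected stay over 48 hours, but it shows the mechanism: among patients who leave the ICU early, rank depends largely on how ill they were on arrival. Between randomised arms, that part of the ranking is noise.

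A fixed weight of 13 removes the baseline contribution only if the later SOFA sum rises by about 13 per baseline point, and nothing in the plan shows that it does. APACHE II, admission category and centre are not in the score, so their prognostic value goes unused whatever that slope is. At stake are some power in a design with no slack, and protection against chance imbalance at the final analysis and the two looks.

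**Working it through.** **1. The plan's sample size.** Two means, 0.33 SD, 90% power, two-sided 0.05: n per arm = 2 × (1.960 + 1.282)² / 0.33² = 193, or 386 in total, against 385 stated. With looks at 150 and 275 and Lan-DeMets O'Brien-Fleming spending, recursive integration gives 392. The figure reproduces within 2%. Recomputed two-sided boundary P values are 0.00066, 0.0158 and 0.0451, against 0.0006, 0.0156 and 0.0452 in 10.3.

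**2. Power with adjustment.** If baseline explains a share R² of the outcome variance, the drift is 0.33 × √(385 × E / (1 − R²)) / 2. E is the rank-test efficiency: 1, or 0.955 for normal data. CDDS is not normal, so E is an assumption too. At R² = 0 and E = 1 the drift is 3.24.

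| R² (assumed) | Power, E = 1 | Power, E = 0.955 | N for 90%, E = 1 |
|---|---|---|---|
| 0 | 89.5% | 88.1% | 392 |
| 0.03 | 90.4% | 89.0% | 380 |
| 0.10 | 92.3% | 91.2% | 353 |
| 0.20 | 94.9% | 94.0% | 313 |
| 0.30 | 97.0% | 96.4% | 274 |

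**3. What R² admission SOFA alone could give.** Let A be admission SOFA, S the day 2–14 sum and ρ their correlation. For CDDS = S − 13A:

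R² = (ρ·sdS − 13·sdA)² / (sdS² + 169·sdA² − 26·ρ·sdS·sdA).

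Take assumed sdA = 3 and sdS = 80.
- ρ = 0: 39² / 7921 = 0.19
- ρ = 0.2: 0.08
- ρ = 0.3: 15² / 6049 = 0.04
- ρ = 0.4: 0.01
- ρ = 0.5: 1² / 4801 = 0.00

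Over sdA 2–4, sdS 60–100 and ρ 0–0.6, R² runs from 0.00 to 0.43. It vanishes where the slope of S on A, ρ·sdS/sdA, is about 13.

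**4. Simulation.** CDDS was simulated under the plan's scoring rules (N = 385, one look, assumed trajectories, 25–35% ICU deaths), comparing the Wilcoxon test with rank ANCOVA. The simulated effect differs from that in step 2, so only the differences matter. Where baseline predicted outcome weakly, power rose from 62% to 76%. Where it predicted strongly, it rose from 83.2% to 83.6%, and to 85.0% with an added APACHE-like covariate. No scenario lost power. Type I error was about 4 to 6% for both tests.

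**5. Chance imbalance.** A 0.5-point difference in mean admission SOFA shifts mean CDDS by 0.5 × (13 − slope). With the SDs in step 3 this is 6.5 points at slope 0 (ρ = 0), 2.5 at slope 8 (ρ = 0.3) and about zero at slope 13.3 (ρ = 0.5). At N = 275 with 1:1 allocation, the standard error of the CDDS difference is 89 × 2/√275 = 10.7 at ρ = 0, so z moves by 6.5/10.7 = 0.61. At ρ = 0.3 it moves by 2.5/9.4 = 0.27, and at ρ = 0.5 by about zero. The futility rule, P > 0.459, corresponds to |z| < 0.74.

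**The case against.** The plan gives a reason for its test, and an unadjusted rank-sum test in a randomised trial is valid. Its P value already allows for chance imbalance in any covariate. This stands: the matter is efficiency, not error.

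The subtraction of admission SOFA already does part of the adjusting. This stands too, and it is why the gain from that covariate may be close to nil. A reader might infer from the weight of 13 that the score over-corrects. The documents do not show that: scoring discharge as 0 flattens the slope of the later sum on baseline, but scoring death as 20 to day 14 steepens it if sicker patients die more often.

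A reader might also take the 6.5-point shift as typical. It is the upper case, reached only if later SOFA is unrelated to baseline, and it is about 6.5/89 = 0.07 SD. With sdA = 3, the standard error of the difference in admission SOFA at N = 385 is 3 × 2/√385 = 0.31, so an imbalance of 0.5 or more has a chance of about 10%.

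Finally, crediting a high admission score is deliberate. A linear ANCOVA of CDDS on admission SOFA gives the same treatment effect as an ANCOVA of the raw SOFA sum, so adjustment weakens that credit in the treatment contrast. This is a real trade-off. It rules out the tempting reading that adjustment gains power at no cost. The reply is that the credit is fixed on arrival, so between randomised arms it carries no treatment effect.

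**Conclusion.** The point holds as one of efficiency and robustness. The primary test is valid but leaves baseline data unused, and the design has no slack: the stated 90% is 89.5% once the looks are counted and 88.1% at a rank efficiency of 0.955. An R² of 0.10 from all covariates together would restore 90% (91.2 to 92.3%), and 0.20 would give 94.0 to 94.9%.

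The direction is well supported, since no simulated scenario lost power or showed inflated type I error. The size is not. The documents contain nothing from which R² can be derived, and in the simulations the gain from admission SOFA alone ran from about 0 to about 14 power points. Converting the gain into a definite number of patients saved would claim more than the documents support.

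**What to change.** Amend 10.2 and 10.3 as follows.

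- Keep CDDS and its ranking. Make the primary test a baseline-adjusted rank analysis, either rank ANCOVA or a proportional-odds model (choose one), with treatment, admission SOFA, APACHE II, admission category (sepsis, trauma/haemorrhage, post-resuscitation, other) and centre.
- Use only covariate values fixed before randomisation. The plan defines no scoring window for admission SOFA or APACHE II, and daily SOFA uses maxima. Section 5.2 allows inclusion up to 12 hours after ICU admission, while 11.2.1 aims to randomise within 2 hours. A first-day worst value could therefore be partly post-randomisation. State the window; if a score cannot be fixed before randomisation, leave it out.
- Apply the same statistic at both interim looks and in the futility rule.
- Report the unadjusted rank-sum test as supportive.

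The cost is protocol wording and a clear baseline window; the covariates are largely collected already. The downsides are a conditional effect measure, less influence for the admission-score credit, and a result slightly harder to explain. If the investigators want that credit to count in full, the adjusted analysis can instead be a prespecified sensitivity analysis, but the primary test then forgoes the gain.
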